## 1.0 GOALS AND OBJECTIVES (SCIENTIFIC AIMS)

### 1.1 Primary Aims

- 1.1.1 To assess whether QMR can accurately and quantitatively assess lymphedema severity. QMR results will be compared to validated, gold standard quantitation of total body, extracellular and intracellular water distribution using deuterium (“heavy water”) and sodium bromide (NaBr) and whole body MRI.
- 1.1.2 To assess tolerability, and define and describe the toxicities of propranolol, administered two times daily in patients with lymphedema both by
- 1.1.2a subjective patient-reported symptoms (energy levels, fatigue, dizziness, respiratory issues/wheezing, activities of daily living) by validated questionnaires (SF-36, LYMPH—ICF, LYMPH—ICF--LL)
- 1.1.2b objective measures (heart rate, blood pressure) by physical exam

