## 2.0 BACKGROUND

	Primary Endpoint (Aim 1)	Secondary Endpoint (Aim 2)
Subjective Assessment	Questionnaires QOL	Questionnaires
	Short Form 36 Lymph-ICF Lymph-ICF-LL	Symptoms (Drainage, pain) Activity levels Clothing size change
Objective Assessment	Clinical and radiological Exam	Clinical and radiological Exam
	Blood pressure Heart rate Blood sugar Whole Body MRI QMR Deuterium and NaBr	Weight, BMI Limb girth discrepancy CTCAE Grading for Lymphedema Imaging: QMR, whole body MRI Blood and Tissues Circulation biomarkers IHC lymphatic vessel phenotype PIK3CA mutational analysis Next Gen sequencing analysis

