At the 2nd-week re-evaluation, they will be escalated to the new dose (1mg/kg/day) if the baselines HR and BP are WNL. Patients will have HR and BP noted after first new dose (1mg/kg/day) of propranolol to ensure that the propranolol is tolerated. If the HR and BP are WNL, they will continue on this new dose and re-evaluated in 2 weeks for the 4th-week evaluation. If they have a drop in HR and BP to below normal range, they will be de-escalated and remain on the prior dose (0.5mg/kg/day) until the next visit (week 4).

At the 4th and 6th-week evaluation, their baseline vitals will be evaluated and their propranolol escalated to the next dose (if vitals are WNL) and have their HR and BP assessed after first new dose. Propranolol will stay increased or held at old dose depending on HR and BP after the first new dose as described above. If on re-evaluation in 2 weeks a patient continues to have below normal HR and blood pressure on re-challenge of the escalated dose, they will not be escalated and remain at the last tolerated dose for the remainder of the 8 week period with no further re-challenges. For patients with below normal HR and BP and needed their doses held, they will be reported as AEs.

At each study visit, patients will be asked to complete validated questionnaire to assess for tolerance to propranolol treatment, subjective changes in lymphedema symptoms, and self-reported function and activities of daily living (SF-36, LYMPH—ICF, and LYMPH—ICF—LL) (See attached documents, Appendix 2). Physical examination will include weight and BMI, vitals (HR, BP), and measurement of girth of normal and affected extremity.

MRIs and blood tests will be performed at study entry and study endpoint to assess for changes in lymphedema tissue composition[21-23] in response to propranolol.

Blood draws will be performed at study entry, at the midpoint, and study endpoint to assess for changes in circulating biomarkers in response to propranolol treatment.

Correlative biomarkers assessed will include markers of progenitor, endothelial, lymphatic, macrophage, and adipocyte cells, and expression of beta-adrenergic receptors (Table 3).

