**Table 6. Study schedule and evaluations**

STUDIES TO BE OBTAINED	Pre-Study	Wk 1	Wk 2	Wk 3	Wk 4	Wk 5	Wk 6	Wk 7	Wk 8
Informed consent	x								
Demographics	x								
Medical history	x								
Questionnaires	x	x	x		x		x		x
Physical exam	x	x	x		x		x		x
LM measurements	x	x	x		x		x		x
Vital signs	x	x	x		x		x		x
Height	x	x	x		x		x		x
Weight	x	x	x		x		x		x
CBC w/diff, platelets	x				x				x
Cr	x				x				x
Blood glucose	x	x a	x a		x a		x a		x a
EKG	x	x a	x a		x a		x a		x a
Echocardiogram a	x								
serum $\beta$ -HCG for females of childbearing potential	x								
Adverse event evaluation	x	x	x	x	x	x	x	x	x
Skin Biopsies	x								x
CXR a	x								
MRI	x								x
QMR	x								x
Body water content evaluation	x								x

aIf clinically indicated after initial evaluation

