## 8.4 Statistical Analysis

Descriptive statistics will be used to summarize patient characteristics, toxicity data, response data and biomarker expression. Toxicity rates at each dose tested will be presented with 95% exact confidence intervals. Responses will be evaluated among patients treated at the highest tolerable dose. Continuous outcomes will be summarized using mean  $\pm$  standard deviation or median (interquartile range) for non-normal data. Comparisons between groups and response changes from baseline will be evaluated using two-sided t-tests or the non-parametric equivalent Wilcoxon Rank-Sum test (for non-normal data). Association between PIK3CA mutational status and patient response will be assessed using chi-square/Fisher exact test. All analyses will be performed using a type I error of 0.05. Biostatistics will be done using Irving Institute for Clinical and Translational Research statistical services at Columbia University Medical Center.

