## 11.2 Study Design/ Endpoints (Table 2)

11.2.1 **Study design:** Each patient will serve as his/her own control, for comparison of study questionnaires (subjective) and with changes in the clinical measurements and imaging measurements of the anatomic area affected by lymphatic malformation compared before and after treatment (objective). In our experience, children exhibiting responses to propranolol displayed these within 2 weeks of beginning propranolol treatment, with estimated reduction in the overall volume of the affected area exceeding 20%.

11.2.2 **Primary endpoints:** The primary endpoint will be the tolerability of escalating dosage of propranolol both by subjective reporting (survey instrument) as well as objective measurements of vital signs. Survey instruments include a general quality of life (QOL) and function survey (SF-36), as well as validated survey instruments for patients with lymphedema (LYMPH—ICF, LYMPH—LCF—LL)[38, 39].

11.2.3 **Secondary endpoints:** The secondary endpoints of the study will be both subjective and objective evaluation of the lymphedema after propranolol treatment, as measured by both survey instrument and objective measurements (clinical exam and radiological studies), as well as biological assays from tissues obtained from biopsies.

11.2.3.1 We will determine whether higher doses of propranolol are well tolerated in this patient population. Secondarily, we will measure determine whether higher doses correlate with improvement in lymphedema symptoms and signs, and healing or improvement of skin lesions, if present (reduced lymphatic leakage, reduced bleeding). Skin lesions will be photographed at clinical visits, and daily lymphatic fluid losses estimated by weight measurements.

Using MRI and body composition analysis, we will determine whether propranolol decreases lymphedema, alters edema water content and location (intracellular vs. interstitial), or alters adiposity of affected extremity.

We will study the biologic activity of oral propranolol against lymphedema, by examining the expression of progenitor cell markers, lymphatic endothelial cell markers, beta-adrenergic receptor expression, macrophage markers and detection of adipocyte content of biopsy specimens (see table below). Results will be compared to ultrasound and magnetic imaging data.

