#### 11.3.2 Imaging Studies

Lymphedema MRI characteristics before and after propranolol therapy will be assessed and related to clinical outcome, as applicable. Specifically, whole body MRI will be used to evaluate body composition and changes in regional adipose tissue depots in the affected limb[21-23].

Furthermore, changes in body composition (water and fat content) in response to propranolol treatment will be evaluated in this study. To evaluate water content, the standard deuterium dilution technique will be used. Fasting patients will have blood draw before drinking stable deuterium isotopes and sodium bromide and after isotope equilibration (about 3-4 hours). Total body water, extra-cellular and intracellular water content can be calculated[22, 40]. Furthermore, a quantitative magnetic resonance (QMR) system will be used to evaluate body (fat and water) content in response to propranolol treatment[21]. Quantification and analysis of results will be performed by [name].

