### **12.0 EVALUATION CRITERIA**

#### 12.1 **Adverse Events**

Any patient who receives the study drug will be evaluable for Adverse Effects. This study will utilize the NIH Common Terminology Criteria for Adverse Events v4.0 (CTCAE) for evaluating adverse events.

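### Blood sugar is listed as a primary objective measure, but every on-treatment glucose test is conditional, so asymptomatic low glucose is not systematically ascertained

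*Combined protocol and SAP*

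**What the plan says.** - **Table 2**, primary-endpoint column, objective row, opens with "Blood pressure Heart rate Blood sugar". Two other places define the objective primary measures more narrowly: Section 1.1.2b has "objective measures (heart rate, blood pressure) by physical exam" and Section 11.2.2 has "objective measurements of vital signs". Neither names glucose.
- **Table 6** schedules a pre-study glucose without condition. Each later glucose entry carries footnote a, "If clinically indicated after initial evaluation". Vital signs have no such condition at the same visits, and neither do CBC and creatinine at Weeks 4 and 8.
- **Table 5** has a row for glucose between 60 and 80 mg/dl without symptoms. It calls for clinical evaluation, a look at feeding, and a repeat test after extra feeds.
- **Section 2.3.2.3** associates hypoglycemia with infants, says this is not established in older patients, and relies on regular eating and on snacks when a patient feels unwell.
- **Section 8.4**: "Toxicity rates at each dose tested will be presented with 95% exact confidence intervals". **Section 12.1**: "Any patient who receives the study drug will be evaluable for Adverse Effects".
- **Section 11.3.2**, on body water: "Fasting patients will have blood draw before drinking stable deuterium isotopes and sodium bromide". Table 6 places this evaluation at pre-study and Week 8.

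**The concern.** A measure in the primary column of the endpoint table would normally be collected from every patient at fixed times. This one has only a baseline value by schedule. Afterwards, a patient without symptoms is tested only if someone decides that there is a reason to.

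Low glucose also belongs to the toxicity question whatever Table 2 says. Aim 1.1.2 is to characterize propranolol's toxicities, the abstract includes hypoglycemia among the drug's potential adverse effects, and Table 7 lists it as a known toxicity. At stake is what the trial can say about low glucose at doses up to 3 mg/kg/day. If untested patients sit in the denominator as event-free, the result is a coherent rate of clinically detected hypoglycemia, but it is not the frequency of low glucose at that dose.

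**Working it through.** The plan states no figure on this point, and its sample size rests on clinical volume. The check is therefore a comparison of texts, followed by arithmetic for illustration and cost.

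**1. Count from Table 6 (on-treatment visits at Weeks 1, 2, 4, 6, 8).**

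| Measure | Scheduled on treatment | Unconditional |
|---|---|---|
| Vital signs | 5 | 5 |
| CBC, creatinine | 2 (Weeks 4, 8) | 2 |
| Glucose | 5 | 0 |

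No other section schedules glucose on treatment. Section 8.1 repeats laboratory work only for a deteriorating patient, and the blood tests in Section 2.4 do not name glucose.

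**2. Table 5 against Table 6.** The 60-80 mg/dl row applies only to a patient without symptoms who has nevertheless been tested. Table 6 permits such a test but does not require one, so ascertainment is unsystematic rather than absent.

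**3. What the rate would mean.** Sections 8.4 and 12.1, read together, suggest a rate over all treated patients at each dose. This is an inference, since neither section states the denominator for glucose. On that reading the numerator holds only cases that prompted a test.

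**4. Illustration of full testing.** Inputs: n = 15 to 20 (Section 11.1) and hypoglycemia at 0.9% (Table 7, from infants, threshold not stated).

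- Exact two-sided 95% upper limit with no low values, 1 − 0.025^(1/n): 21.8% for 0/15 and 16.8% for 0/20. Fewer patients may reach 3 mg/kg/day, which would widen this.
- Expected cases at 0.9%: 15 × 0.009 = 0.135 and 20 × 0.009 = 0.18. Chance of any: 1 − 0.991^15 = 12.7% and 1 − 0.991^20 = 16.5%. Few clinical cases are to be expected.
- The documents give no frequency for asymptomatic glucose below 80 mg/dl. For assumed values p, the chance of finding at least one if everyone is tested is 1 − (1 − p)^n:

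| Assumed p | n = 15 | n = 20 |
|---|---|---|
| 5% | 53.7% | 64.2% |
| 10% | 79.4% | 87.8% |
| 20% | 96.5% | 98.8% |

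The matching figure under for-cause testing cannot be derived, because neither the number tested nor the reasons for testing are known in advance. An exact interval on a for-cause subset would not describe the treated population either, so none is given.

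**5. Doses that existing draws can cover.** Section 2.4 says "Blood draws will be performed at study entry, at the midpoint, and study endpoint", and Table 6 has CBC and creatinine at Weeks 4 and 8. Under Section 5.1, a Week 4 sample taken before the escalated dose reflects 1 mg/kg/day nominally, and a Week 8 sample reflects 3 mg/kg/day. The 0.5 and 2 mg/kg/day levels have no such draw.

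**6. Cost.** Assays: 15 × 2 = 30 to 20 × 2 = 40. If 5% to 20% of values fall between 60 and 80 mg/dl (assumption), Table 5 adds 0.05 × 30 = 1.5 to 0.20 × 40 = 8 repeat samples over the whole study.

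**The case against.** The strongest reply is that for-cause testing is a deliberate and coherent design, and that Table 2 is simply a loose list of instruments. There is good support for this. Adverse events are evaluated every week in Table 6, and EKG carries the same footnote as glucose. Parents of patients aged 12-18 are told the signs of hypoglycemia (Section 9.1.6), and patients are encouraged to report problems (Section 14.2.2). In intercurrent illness, propranolol is held until oral intake is tolerated (Section 2.3.2.3). All of this stands, and it is why keeping for-cause testing remains an acceptable choice.

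Three further limits also stand:

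- Nothing says that an asymptomatic value of 60-80 mg/dl counts as a toxicity under Section 8.4. Table 5 gives dosing guidance, toxicities are graded by CTCAE, and the row itself requires no dose change.
- Testing at Weeks 4 and 8 leaves two of the four dose levels tested for cause. The Week 8 value comes at the end of therapy and cannot guide study dosing.
- The fasting body-water draw is not shown to be a hazard. The plan does not say whether fasting continues through the 3-4 hour equilibration.

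A reader might infer that Tables 5 and 6 contradict each other, or that hypoglycemia would go undetected. The documents support neither. A clinical indication is wider than symptoms, and illness or poor intake could prompt a test in a patient without hypoglycemic symptoms. What the reply leaves unanswered is that blood sugar is still listed as a primary measure without systematic data behind it.

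**Conclusion.** The point holds in limited form. Table 2 names a measure that Table 6 does not collect systematically on treatment: none of the five on-treatment glucose tests is required. Asymptomatic low glucose will be found by discretion or chance, and any reported rate is one of clinically detected hypoglycemia.

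A reader might go further and conclude that a primary endpoint is compromised. The documents do not support that. Sections 1.1.2b and 11.2.2 confine the objective measures to heart rate, blood pressure or vital signs, and vital signs are taken unconditionally at every visit. Only Table 2 would need correcting.

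Nor can the probabilities of 53.7% to 98.8% be read as the size of the loss. They rest on assumed prevalences and have no for-cause counterpart. The loss is not quantifiable from the plan. This is a cheap improvement to safety description, not a repair on which the primary analysis depends.

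**What to change.** **Preferred: routine glucose at two visits.**

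1. Before it starts, close a gap in Table 5, which as it reads has no action for asymptomatic glucose of 60 mg/dl or below. Specify at least the evaluation and repeat test of the 60-80 row. The clinical team should decide whether propranolol is held.
2. Remove footnote a from glucose at Weeks 4 and 8 and run the assay on the CBC/creatinine blood. Take the Week 4 sample before any escalated dose.
3. Record fasting status and time since last dose with every value, including baseline.
4. Report low values over patients tested, by the dose actually taken, and state that 0.5 and 2 mg/kg/day are tested for cause only.

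The cost is 30-40 assays with no extra visit or needle-stick for the first test, plus a few repeat samples. Week 4 and Week 8 values cannot validly be compared as a dose effect if fasting state differs.

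**Alternative: keep for-cause testing.** Remove blood sugar from the primary column of Table 2. Report it as clinically detected hypoglycemia with the number of patients tested, and do not present an exact interval on that subset as a population rate. The cost is a wording change.

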## 8.2 Correlative Studies

### 8.2.1 Description of Studies

Correlative biology studies will include markers for progenitor, endothelial, lymphatic, macrophage, and adipocyte identity, and expression of beta-adrenergic receptors.

### 8.2.2 Sampling Schedule

In patients with skin lesions on the affected extremity, skin biopsy samples will be collected at study entry and at the two-month evaluation point (Week 8).

### 8.2.3 Sample Labeling

Each biopsy specimen must be labeled with the patient's study registration number and the date and time the sample was taken. Data should be recorded on the Correlative Study Form (Appendix 1).

## 8.3 Radiology Review

MRIs to be reviewed for comparison and analysis by [name].

## 8.4 Statistical Analysis

Descriptive statistics will be used to summarize patient characteristics, toxicity data, response data and biomarker expression. Toxicity rates at each dose tested will be presented with 95% exact confidence intervals. Responses will be evaluated among patients treated at the highest tolerable dose. Continuous outcomes will be summarized using mean  $\pm$  standard deviation or median (interquartile range) for non-normal data. Comparisons between groups and response changes from baseline will be evaluated using two-sided t-tests or the non-parametric equivalent Wilcoxon Rank-Sum test (for non-normal data). Association between PIK3CA mutational status and patient response will be assessed using chi-square/Fisher exact test. All analyses will be performed using a type I error of 0.05. Biostatistics will be done using Irving Institute for Clinical and Translational Research statistical services at Columbia University Medical Center.

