#### **2.3.2.3 Hypoglycemia:**

Propranolol has been reported to cause hypoglycemia in infants treated with propranolol. While these data is not established in old patients, all study patients will be encouraged to keep a regular food schedule and snack if they feel fatigued or dizzy.

If patients become ill for other reasons during the study period (eg URIs, gastroenteritis) during the study period, they are encouraged to contact us. Their propranolol dose will be held until they are able to tolerate POs.

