**Table 1**

**Table 1. Propranolol intra-patient dose escalation schedule and assessments**

	Propranolol	Assessments		
		Subjective	Objective	Other
Week 1 (initiation)	0.5 mg/kg/day, divided bid	Entrance Interview Quality of Life Questionnaire	Physical Exam, Imaging	Blood Draw, a Tissue Biopsy a
Week 2	1 mg/kg/day, divided bid a,b	Quality of Life Questionnaire	Physical Exam	
Week 4	2 mg/kg/day, divided bid a,b	Quality of Life Questionnaire	Physical Exam	Blood Draw
Week 6	3 mg/kg/day, divided bid a,b	Quality of Life Questionnaire	Physical Exam	
Week 8	3 mg/kg/day, divided bid a,b	Exit Interview, Quality of Life Questionnaire	Physical Exam, Imaging	Blood Draw, a Tissue Biopsy a

aWeight rounded to the nearest 10-kg increment

bDose escalation in the absence of clinical contraindications.

bIn the presence of clinical contra-indications, the patients will remain on their current level of dosage, or decreased to the previous level, or have their medications held.

A maximum of 8-weeks of therapy may be administered

Studies have shown that the peak effect of oral propranolol on blood pressure and heart rate occurs 1 to 3 hours after it is taken. As such, current recommendations are that patients should have HR and BP done at baseline and also hourly for the first 2 hours after a dose increase, and at least once after the target dose is achieved. As dose response is generally most significant after the first dose, once normal vitals are obtained with the first dose there is no recommendation that vitals should be re-checked at the same dose level, unless the patient is very young, has cardiovascular issues or co-morbidities, or if clinical complaints arise.

Patients must have vitals within the normal range for their age group prior to starting in the study. After the first dose (0.5mg/kg/day), they will be re-evaluated. If their heart rate (HR) and blood pressure (BP) are within normal limits (WNL), they will continue on this dose for the next week until the next evaluation. If there is a fall below normal range (>15%) of HR and BP, they will rest off medications for 2 weeks and re-challenged. If they tolerate the dose, they will continue on the study. If they cannot tolerate the lowest dose for the 2nd time, they will be removed from the study, as they cannot tolerate the lowest dose.

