## **5.0 TREATMENT PROGRAM**

### **5.1 Overview of Treatment Plan**

Patients will be provided with propranolol prescriptions. Dosing is weight-based (corrected to the closest 10kg increment) and will be prescribed by the PI after medical evaluation by the study cardiologist.

The starting dose of propranolol will be 0.5 mg/kg/day, which is the current institutional dose for initial treatment for cardiovascular and hemangioma indications in children. Dose escalation to 1 mg/kg/day will take place at the 2-week evaluation in the absence of clinical contraindications. If patient tolerates 1 mg/kg/day dose, they will be escalated to 2 mg/kg/day at the 4-week evaluation. In the absence of clinical contraindications, dose escalation will be increased to 3mg/kg/day at week 6 and continued for the duration of the study. A maximum of 8-weeks of therapy may be administered.

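### Crude toxicity rates at each dose can differ without a dose effect, because time on dose is unequal and section 8.4 makes no allowance for it

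*Combined protocol and SAP*

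**What the plan says.** Tolerability of escalating propranolol is a primary endpoint (aim 1.1.2 and section 11.2.2). The only toxicity analysis by dose is one sentence in section 8.4: "Toxicity rates at each dose tested will be presented with 95% exact confidence intervals". It does not define the denominator or the time at risk. It also does not say to which dose an event belongs after a hold, a de-escalation or a re-challenge.

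Several places determine how long a patient spends at each dose:

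- **Starting dose.** Table 1 puts 0.5 mg/kg/day at Week 1 and 1 mg/kg/day at Week 2. Section 2.4 agrees: after a tolerated first dose, "they will continue on this dose for the next week until the next evaluation". Section 5.1 says "Dose escalation to 1 mg/kg/day will take place at the 2-week evaluation in the absence of clinical contraindications", which can be read as two weeks at 0.5.
- **Higher doses.** Steps are two weeks apart (Weeks 2, 4 and 6). At the top, "dose escalation will be increased to 3mg/kg/day at week 6 and continued for the duration of the study". Therapy is capped at 8 weeks.
- **Failed escalation.** Under section 2.4, a patient who fails the re-challenge will "remain at the last tolerated dose for the remainder of the 8 week period with no further re-challenges". Section 5.2.2 has a similar rule.
- **Holds.** For intercurrent illness, section 2.3.2.3 says "Their propranolol dose will be held until they are able to tolerate POs".

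Table 6 schedules CBC and creatinine on treatment at Weeks 4 and 8 only. Adverse event evaluation is weekly. Vital signs and questionnaires are at Weeks 1, 2, 4, 6 and 8. Glucose and EKG are listed at those same visits, if clinically indicated.

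**The concern.** A proportion of patients with an event describes tolerability fairly across doses only if each dose is observed for a similar time, or if the event does not depend on time. Neither is assured here. A toxicity that builds up with days on drug, such as sleep disturbance or somnolence from Table 7, has more time to appear at a dose held for six weeks than at one taken for one or two.

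At stake is the descriptive by-dose result for a primary endpoint. A short starting period can make the first step up look more toxic than it is. Patients parked at a low dose can make that dose look worse than the doses above it. A reader cannot undo either effect unless days on dose are reported.

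**Working it through.** **1. The plan's own total.** The stated maximum is 8 weeks = 56 days. Three readings of the week numbers give these days at 0.5 / 1 / 2 / 3 mg/kg/day:

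| Reading | Days per dose | Sum |
|---|---|---|
| A: Table 1 visit weeks, stopping at the Week 8 visit | 7 / 14 / 14 / 14 | 49 |
| B: escalation to 1 mg/kg/day at day 14 (section 5.1) | 14 / 14 / 14 / 14 | 56 |
| C: Table 1 visit weeks, therapy to the end of Week 8 | 7 / 14 / 14 / 21 | 56 |

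B and C reach 56 days. A is 7 days short. The documents do not settle which is meant.

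**2. Held patients.** A patient who reaches 1 mg/kg/day and fails escalation stays there from Week 2 to Week 8: (8 − 2) × 7 = 42 days under A, and 56 − 14 = 42 days under B. Under C it is 56 − 7 = 49. I use 42. A patient held at 2 mg/kg/day from Week 4 to Week 8 has 28 days. For a patient who twice fails escalation to 1 mg/kg/day, sections 2.4 and 5.2.2 (hold) and 14.2.3 (removal) disagree, so time at 0.5 is also undefined.

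**3. Crude risk with no dose effect.** The documents give no toxicity hazard by dose. Assume the same 7-day risk p at every dose, constant over time. The risk over d days is R(d) = 1 − (1 − p)^(d/7).

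| p (assumed) | 7 days | 14 days | 42 days |
|---|---|---|---|
| 2% | 2.0% | 3.96% | 11.4% |
| 5% | 5.0% | 1 − 0.95² = 9.75% | 1 − 0.95⁶ = 26.5% |
| 10% | 10.0% | 19.0% | 46.9% |

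For full escalators at p = 5%, the four crude rates are:
- A: 5.0 / 9.75 / 9.75 / 9.75%
- B: 9.75% at every dose
- C: 5.0 / 9.75 / 9.75 / 14.3% (1 − 0.95³ = 14.3%)

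**4. Effect of held patients on the dose-level rate.** Assume 25% of patients are held at 1 mg/kg/day for 42 days and the rest spend 14 days there. Do not count a single failed test dose as time at 2 mg/kg/day.
- p = 5%: 0.75 × 9.75% + 0.25 × 26.5% = 13.9%, against 9.75% at a dose taken for 14 days.
- p = 10%: 0.75 × 19.0% + 0.25 × 46.9% = 26.0%, against 19.0%.
- If 10% are held (p = 5%): 11.4%.

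Events per patient-week would be the same at every dose: −ln(0.95) = 0.051 at p = 5%.

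**5. Precision.** With 15–20 patients, exact binomial 95% intervals are 0.1%–24.9% for 1/20, 1.2%–31.7% for 2/20 and 0.2%–31.9% for 1/15. Treating doses as independent groups of 20 (a rough device, since the same patients contribute to each), power to detect 5% against 9.75% is about 8%.

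**6. Laboratory coverage.** For a full escalator, the Week 8 draw of CBC and creatinine falls on 3 mg/kg/day. The Week 4 draw falls on 1 mg/kg/day if taken before that visit's escalation, and on 2 if taken after. The order is not stated. Either way, routine draws cover two of the four doses.

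**The case against.** The best defence has four parts.

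- **The toxicity summary is descriptive.** No between-dose toxicity test is named, and the artefact would rarely stand out against intervals this wide. That is correct and limits the harm. It does not justify rates that cannot be interpreted without exposure.
- **Heart rate and blood pressure are the objective tolerability measures.** Section 2.3.2.1 says their response is generally greatest after the first dose, and they are checked after the first dose at each level. Such events need not grow with days, so the constant-hazard arithmetic does not apply to them. This stands.
- **The starting period may be 14 days.** If so, full escalators have equal time at all four doses. A reader might infer from Table 1 that the rate necessarily about doubles from 0.5 to 1 mg/kg/day. The documents do not support that as a certainty: it depends on the 7-day reading and on time-accruing events. The imbalance from held patients remains.
- **Ascertainment covers every dose.** A reader might infer that laboratory toxicity at 0.5 and 2 mg/kg/day is zero by construction. It is not. Glucose can be taken at any dose visit if indicated, and sections 4.0 and 8.1 call for repeat laboratory tests before the next escalation in a deteriorating patient. Only routine CBC and creatinine are limited. A reader might also infer from the exit interview in Table 1 that symptoms are elicited only at Week 8 on the top dose. Questionnaires at every study visit and weekly adverse event evaluation contradict that.

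Patient-time is not a complete cure. It does not remove the selection of intolerant patients into held doses or the confounding of dose with calendar order.

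**Conclusion.** The concern holds for toxicities that accrue with time. The plan reports crude rates by dose although a patient held at 1 mg/kg/day has 42 days there against 14 scheduled, and the starting period is 7 or 14 days depending on the section. With no dose effect and an assumed constant 7-day risk of 5%, the risk is 5.0% over 7 days, 9.75% over 14 and 26.5% over 42. The 26.5% is one held patient's risk, not a dose-level rate. At the dose level the distortion is about 13.9% against 9.75%, if 25% are held. The hazard and the held fraction are assumptions; the documents give neither.

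The conclusion does not extend to heart-rate and blood-pressure events at the first dose of a level, and it is not a claim that the rates must differ. Routine CBC and creatinine do not cover all doses, but the other safety assessments do. Given the sample size, this is a worthwhile and cheap correction to a descriptive primary result, not a flaw that invalidates the study.

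**What to change.** In section 8.4, for each dose:

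- Report the number of patients treated, the number of events and the patient-days on that dose, excluding holds. Attribute each event to the dose being taken at onset.
- For time-accruing events, give events per patient-week with an exact Poisson interval.
- For between-dose description, and for heart-rate and blood-pressure events, give the proportion with an exact binomial interval in a common window from the first dose at each level. The first 7 days would do, as the shortest scheduled period under any reading.
- Report CBC and creatinine toxicity over the number of patients actually tested at that dose.
- State as limits that held patients are selected for intolerance and that dose is confounded with calendar order.

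Reconcile sections 2.4 and 5.1 on the length of the starting-dose period, and sections 2.4, 5.2.2 and 14.2.3 on patients who fail escalation to 1 mg/kg/day, so that the denominators are defined.

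The cost is SAP wording plus the recording of dose start, stop and hold dates. No sample size change is needed. The windowed comparison uses fewer events, so its intervals will be slightly wider.
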